#### Pause / Nurse Call-back

- At any screen the parent may request to pause for a call back.
- The platform flags a call-back task to the study nurse within 24 h; progress is locked until the nurse
  documents that outstanding questions were answered.
- This satisfies the GCP requirement that the subject (guardian) has "adequate time and opportunity to ask questions" (GCP 4.8.6).

## **Optional Face-to-Face Consent at Site**

- Parents may instead choose in-clinic consent.
- Site staff give the paper PIS/ICF or display the same PIS on a tablet, answer questions, witness wet or stylus signature, and upload the signed form to the eISF.
- Both routes generate identical consent content; only the mode of signature differs, meeting MHRA/HRA equivalence expectations.
  - Regulatory Compliance & Record-keeping
- Audit trail: every consent-related action (view, pause, sign, withdraw) is date-/time-/user-stamped and exportable for inspection.
- **Version control**: if the PIS/ICF is amended, the system locks further enrolments until the updated version is uploaded and the REC has approved.

- Data security: pseudonymised IDs are used; personal identifiers are encrypted at rest and in transit (AES-256, TLS 1.2).
- Copies of all consent documents are retained for at least 25 years post-trial (per UK SI 2004 Reg 31A).

The consent process—digital or paper—fulfils all elements of informed consent (content, comprehension, voluntariness, documentation), meeting **GCP**, **MHRA** and **REC** requirements.

#### Confirmation of Ongoing Consent & Eligibility at First In-Person Visit

At the participant's first in-person visit (Day 0), the Investigator or delegated site staff will:

#### 1. Re-confirm Informed Consent

- a. Verify that the parent/legal guardian still consents to their child's participation.
- b. Provide an opportunity to ask any further questions, and document continued consent by countersigning the ICF (or updating the eConsent record).

### 2. Review Eligibility Criteria

- a. Confirm that all inclusion criteria remain met (e.g., age 12–23 months; parent/guardian able to comply).
- b. Re-assess key exclusion criteria (e.g., no acute respiratory illness, no fever > 37.8 °C at Visit 1; no recent receipt of excluded vaccines or investigational products).
- c. Any changes that render the child ineligible must be documented, and the child must not be enrolled or randomised.

## 3. Document Findings

- a. Record confirmation of ongoing consent and eligibility in the Source Data and on the Visit 1 eCRF.
- b. If any uncertainty arises, the child's enrolment is deferred until eligibility and consent are satisfactorily confirmed.

#### 12.2.2 Screening

During the eligibility check, if written consent is obtained then the participant's parent/legal guardian will complete a screening questionnaire online to check their eligibility for the study. Time period sensitive criteria will be re-checked in person at visit one.

The eligibility of the child will be reviewed by a suitable member of the clinical team. Decisions to exclude from enrolling in the trial or to withdraw a participant will be at the discretion of the investigator.

As per Section "Temporary exclusion criteria": If a child has an acute respiratory illness (moderate or severe illness with/without fever) or a fever (oral temperature > 37.8°C) at Visit 1 Screening, the child will not be enrolled that day, but may be considered for enrolment at a later date if they recover in sufficient time.

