## 11.3.1 Temporary exclusion criteria

If at Visit 1 Screening & Vaccination the volunteer has any of the following, they will not be enrolled that day.

- Acute respiratory illness with or without wheeze (moderate or severe illness with or without fever)
- Fever (oral temperature greater than 37.8°C)
- Active wheezing at the time of dosing/randomisation (including use of bronchodilators within the past 72 hours).

They may be considered for enrolment later in the trial if they recover in sufficient time.

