## 12.4 Blinding and code-breaking

Participants' parents/legal guardians and analysing statisticians will remain blind to treatment allocation. Clinical staff involved in study delivery will be aware of which vaccine the participant is receiving (arm allocation). To maintain blinding as much as possible from attending healthcare providers during the study, arm allocation will be concealed from other healthcare provider contacts via the electronic case report form and will only be visible to site staff at the time data is being entered during a vaccination visit.

If the clinical condition of a child necessitates unblinding to vaccine or placebo allocation, the local investigator will have unrestricted and immediate access to break the treatment code via the participants electronic case report form if they find it is in the best interest of the trial subject. This will be done if unblinding is thought to be relevant and likely to change clinical management.

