## 12.6 Early Discontinuation/Withdrawal of Participants

In accordance with the principles of the current revision of the Declaration of Helsinki and any other applicable regulations, a participants' parents/legal guardian has the right to withdraw them from the study at any time and for any reason, and are not obliged to give their reasons for doing so. The Investigator may withdraw the participant at any time in the interests of the participants' health and well-being. In addition, the participant may withdraw/be withdrawn for any of the following reasons:

- Administrative decision by the Investigator
- Ineligibility (either arising during the study or retrospectively, having been overlooked at screening).
- Significant protocol deviation

- Participant non-compliance with study requirements
- An AE, which requires discontinuation of the study involvement or results in inability to continue to comply with study procedures

The reason for withdrawal will be recorded in the CRF. If withdrawal is due to an AE, appropriate follow-up visits or medical care will be arranged, with the agreement of the volunteer, until the AE has resolved, stabilised or a non-trial related causality has been assigned. The DSMB or DSMB chair may recommend withdrawal of participants.

In cases of subject withdrawal, long-term safety data collection may continue as appropriate if subjects have received one or more vaccine doses, unless they decline any further follow-up.

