## 13.1.3 Blinding of IMPs

As the investigators are unblinded there will be no blinding of IMPs, however specific instructions will be given to sites to ensure the participant's parent/legal guardian are unable to see which of vaccine or placebo is being given to their child. Specific site training will explain how vaccine/placebo should be handled and the positioning of parent/carer and child to avoid unblinding of the parent/carer.

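### Staff who know which product is due decide at Day 28 whether to give it, and the primary population depends on that decision, so the comparison can be biased in either direction

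*Protocol*

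**What the plan says.** **Who knows the product.** Protocol 13.1.3 says: "As the investigators are unblinded there will be no blinding of IMPs". Section 12.4 keeps parents and analysing statisticians blind. Its eCRF concealment is aimed at other healthcare providers; the allocation "will only be visible to site staff at the time data is being entered during a vaccination visit". Under 10.1.4 and 10.1.5, the Day 28 product is saline for the early-vaccine (EV) group and LAIV for the late-vaccine (LV) group.

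**Who decides.** Section 12.2.2 says: "Decisions to exclude from enrolling in the trial or to withdraw a participant will be at the discretion of the investigator". Section 12.6 adds: "The Investigator may withdraw the participant at any time in the interests of the" child's health and well-being. Its further list of reasons includes "Administrative decision by the Investigator". The reason for withdrawal goes into the CRF.

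**Which checks apply.** Section 11.3.1 opens its list of respiratory illness, fever and active wheeze with: "If at Visit 1 Screening & Vaccination the volunteer has any of the following, they will not be enrolled that day". Section 12.2.2 adds: "Time period sensitive criteria will be re-checked in person at visit one". For Day 28 the schedules in Appendix A give a visit window and a consent entry. They give no check that governs whether the second product is given.

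**Who is analysed.** Section 15.1 uses both 28-day periods in the primary analysis. Section 15.2 defines the primary population by receipt at Day 0 and at Day 28, and analyses by vaccine received. It also describes the proportions in terms of children dosed at the start of each period. That sentence says numerator where denominator is evidently meant.

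**The concern.** Randomisation at Day 0 does not protect the second period from selection that happens later with the product known. Two children may present identically at Day 28, with a cold or after a wheeze in period 1. Staff may judge them differently when a live vaccine is due rather than saline. The trial exists because of a possible wheeze signal after LAIV (section 6), and recruitment is enriched for children with a wheeze history (12.1.1), so the incentive is plausible.

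If non-receipt at Day 28 differs by sequence, the children contributing LAIV and placebo periods are no longer comparable. The primary relative risk (RR) of a safety trial is then biased by an amount that its confidence interval does not reflect.

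**Working it through.** **1. The plan's own figure.** Inputs from 15.1: placebo risk p1 = 0.9%, RR 2 so p2 = 1.8%, two-sided alpha 0.05, power 80%. The mean risk is 1.35% and the difference d is 0.009.

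- Pooled two-proportion formula: n = [1.960·√(2 × 0.0135 × 0.9865) + 0.842·√(0.009 × 0.991 + 0.018 × 0.982)]² / 0.009² = 2580.
- With continuity correction: n' = (n/4)·[1 + √(1 + 4/(n·d))]² = 645 × (1 + 1.083)² ≈ 2798.

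This matches the stated 2800. It is a number of observations per product, with every child counted once under each. The planned power therefore relies on Day 28 dosing. Period 1 alone has 57% power at 1500 per arm.

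**2. Denominator of children dosed at the start of each period.** Assumptions, not in the documents: 10% of the 1500 LV children (150) are unwell at Day 28 with a 3% 28-day placebo risk; overall placebo risk is 0.9%; nobody is held back from saline. If w LV children do not receive LAIV, the LAIV risk is RR × (27 − 0.03w)/(3000 − w), where 27 = 3000 × 0.009. The placebo risk stays at 0.9%.

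| Share of the 150 held back | w | LAIV risk at true RR 2 | Observed RR | Power |
|---|---|---|---|---|
| 0% | 0 | 1.80% | 2.00 | 86% |
| 10% | 15 | 1.78% | 1.98 | 84% |
| 25% | 37.5 | 1.75% | 1.94 | 82% |
| 50% | 75 | 1.69% | 1.88 | 77% |
| 100% | 150 | 1.58% | 1.75 | 65% |

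For w = 75: 2 × (27 − 2.25)/2925 = 1.69%, and 1.69/0.90 = 1.88. At a true RR of 1, w = 75 and w = 150 give 0.94 and 0.88. Power is the normal approximation at 3000 observations per product before omissions. At the planned 2800 it starts from 83%.

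**3. Strict both-doses population, selection on stable risk.** A held-back LV child now loses the period-1 placebo record as well. If the 3% is a lasting trait, placebo risk is (27 − 0.03w)/(3000 − w) and LAIV risk is twice that. The RR is exactly 2.00. Power is 82% at w = 75 and 79% at w = 150.

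**4. Strict both-doses population, selection on wheeze in period 1.** About 1500 × 0.009 = 13.5 LV children wheeze on placebo. Suppose half (6.75) are held back and the repeat-wheeze risk is 0.9%.

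- LAIV events: 27 (EV, period 1) + 0.018 × 1493.25 = 26.88 (LV, period 2), total 53.88.
- Placebo events: 6.75 (LV, period 1, after exclusions) + 13.5 (EV, period 2) = 20.25.
- Both products have 2993.25 observations, so RR = 53.88/20.25 = 2.66.

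For assumed repeat risks of 0.9% to 10%, the RR is 2.1 to 2.3 with a quarter held back and 2.4 to 2.7 with half held back. With nobody held back, the same model gives 1.9 to 2.0.

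**The case against.** The strongest reply is that a reader might infer a bias that always pulls the RR down and hides an excess of wheeze. The documents do not support that. Section 15.2's both-doses population removes the held-back child's placebo record too, so the RR can stay at 2 or rise. This stands in full: no direction should be claimed.

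A reader might also infer that children can be held back from LAIV but not from saline. No such rule exists. The discretion in 12.2.2 and 12.6 covers both sequences alike. The asymmetry is one that unblinding permits, and nothing shows that it will occur or how often. Nor does postponement within the Day 28 window remove anyone from the analysis; only omission does.

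The larger effects need half or all of the unwell LV children, and no EV children, to be held back. At 10% or 25% held back, power stays above the planned 80%.

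There are partial safeguards: withdrawal reasons are recorded and follow-up may continue (12.6), causes of missing data are to be investigated (15.4), and proportions are shown by period (15.2). None of these conceals the product when the decision is taken or keeps the child in the primary population. The sentence in 12.2.2 sits under screening, so 12.6 is the firmer basis for discretion after enrolment.

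**Conclusion.** The concern holds as a structural weakness. A discretionary decision, made after randomisation by staff who know the product, determines entry to the primary population, and no written Day 28 check common to both sequences limits it. Non-receipt can differ by sequence and bias the primary comparison.

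Size and sign rest on assumed inputs and on which of 15.2's two descriptions of the denominator is applied. By period, a true RR of 2 reads between 1.98 and 1.75 as the share held back goes from 10% to 100% of the assumed 150 children. In the strict both-doses population it stays at 2.00 for selection on stable risk, with some loss of power, and exceeds 2 if children who wheezed on placebo are held back. An unknown direction is no reassurance in a safety trial. An analysis plan cannot repair the conduct of the decision afterwards.

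**What to change.** None of the following sets or changes a clinical criterion.

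- **12.4 and 12.6:** have the Day 28 decision to proceed, postpone or omit, with its reason, entered and locked in the eCRF before the Visit 2 product is displayed. Where possible, it should be entered by a team member who did not give the Day 0 product. Section 12.4 already controls when allocation is visible, so this mainly changes the screen order.
- **15.2:** report Day 28 non-receipt by sequence and reason beside the primary result. Add a period-1 comparison as randomised that keeps every child dosed at Day 0, whether or not dosed at Day 28.
- **11.3.1 and 12.2.2:** the sponsor should reconcile illness checks written only for Visit 1 with a second dosing visit at Day 28. What those checks should be is a clinical matter outside this review.

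The cost is an eCRF screen order, a few sentences, one table and one further comparison. Concealment is only partial where staff recall the Day 0 product, which is why the by-sequence table is needed. The period-1 comparison has about 57% power at 1500 per arm, so it is a check and not a replacement for the primary analysis.

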#### 12.3 Randomisation

Computer generated randomisation list will be prepared by the study statistician and will be performed within the electronic case report form at visit one.

## 12.4 Blinding and code-breaking

Participants' parents/legal guardians and analysing statisticians will remain blind to treatment allocation. Clinical staff involved in study delivery will be aware of which vaccine the participant is receiving (arm allocation). To maintain blinding as much as possible from attending healthcare providers during the study, arm allocation will be concealed from other healthcare provider contacts via the electronic case report form and will only be visible to site staff at the time data is being entered during a vaccination visit.

If the clinical condition of a child necessitates unblinding to vaccine or placebo allocation, the local investigator will have unrestricted and immediate access to break the treatment code via the participants electronic case report form if they find it is in the best interest of the trial subject. This will be done if unblinding is thought to be relevant and likely to change clinical management.

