## 9.1 Outcome ascertainment

Outcomes will be collected from routine GP medical records by the digital CRO, uMed. For medically attended wheeze, specific codes referring to a diagnosis of "Viral induced wheeze" and "Asthma" will be used, alongside findings of "Wheeze", and any new prescription for either Salbutamol or Ipratropium Bromide:

- 276191000000107 | Viral wheeze (disorder)
- 195967001 | Asthma (disorder)
- 56018004 | Wheezing (finding)
- 24612001 | Wheeze rhonchi (finding)
- 372897005 | Salbutamol (substance)
- 372518007 | Ipratropium (substance)

Whilst using codes of a finding of "wheeze" are most specific to the primary outcome, these codes are rarely used in practice and yield insufficient events. GP EPR data from a 3 month period indicates that, "Viral induced wheeze", and "Asthma" are the codes most commonly associated with wheezing. This

yields a population incidence of roughly 2% during a three-month period, in line with the power calculations for the study.

The primary outcome includes all events coded with a finding of "wheeze" together with the addition codes asthma/viral wheeze/salbutamol/ipratropium.

Additional medical attendances at locations other than the child's primary GP practice (e.g., hospital or other GP locations) will be determined using electronic diaries and solicited at follow up visits.

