## 12.5 Visits

The study visits and procedures will be undertaken by one of the clinical trials team. The procedures to be included in each visit are documented in the schedule of attendances (see Appendix A). Each visit is assigned a time-point and a window period, within which the visit will be conducted. If a participant cannot attend a visit, where possible, this will be re-arranged to an in-person visit within the time window. The final visit will be conducted via a digital questionnaire administered by uMed. If the questionnaire has not been completed following additional prompts by the uMed nursing delegate, then the local study team will be contacted to attempt reach out to the participant's family.

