## 14.6 Procedures for Reporting Adverse Events

## 14.6.1 Medically attended AEs

A medically attended AE, is defined as any adverse event for which the participants' parents/legal guardians seeks medical attention for them either at hospital or from primary care. Participants' parents/legal guardians will be asked to record any medically attended AEs on their electronic diary. Medically attended AEs occurring up to 56 days post randomisation, will be directly solicited and reviewed at each study visit.

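### Part of the primary outcome, wheeze attended outside the child's own GP practice, is asked about at D28 by staff who can see the allocation; any bias is probably small and of unknown direction, and the route is cheap to close

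*Protocol*

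**What the plan says.** The main source of the primary outcome is remote. Section 9.1 states: "Outcomes will be collected from routine GP medical records by the digital CRO, uMed". Attendances elsewhere, such as hospital or another GP location, "will be determined using electronic diaries and solicited at follow up visits". Section 14.6.1 adds that medically attended adverse events up to day 56 "will be directly solicited and reviewed at each study visit".

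Diary requests go out 7 and 14 days after each in-person visit (Section 12.5.2).

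Period 1 closes at D28. This visit is in person and run by the trials team (Section 12.5). Safety information is collected there and the other product is given (Section 3, Brief Summary). Section 12.4 says that delivery staff know the arm and that the allocation in the eCRF "will only be visible to site staff at the time data is being entered during a vaccination visit". Blinding is claimed for others: "Participants' parents/legal guardians and analysing statisticians will remain blind to treatment allocation".

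Period 2 closes differently: "The final visit will be conducted via a digital questionnaire administered by uMed". The local team contacts the family only if the questionnaire stays uncompleted after prompts (Section 12.5).

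The protocol does not require the D28 questions to be asked by a blinded person, or answered before the allocation is shown.

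**The concern.** The protocol takes care to keep parents blind and to conceal the arm from attending healthcare providers. The staff who solicit one component of the primary outcome at D28 are left out of that protection. They know the product when they ask about attendances, decide how far to prompt, and enter the answer. Any difference in questioning by product enters the first-period comparison directly and the pooled comparison at about half strength.

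Two consequences follow. An excess of wheeze after LAIV, or its absence, could be challenged on the ground that part of the outcome was elicited unblinded, in a trial meant to inform JCVI policy. Such a difference is also a product-by-period effect, which a two-period, two-sequence design cannot separate from sequence or carry-over. If the carry-over check in Section 15.2 leads to the periods being compared separately, period 1 carries the bias undiluted.

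**Working it through.** **1. The plan's own figure (Section 15.1).** Inputs: 0.9% after placebo, relative risk 2 (so 1.8% after LAIV), 80% power, two-sided 0.05. The two-proportion formula with continuity correction gives 2798 per condition; each child contributes to both conditions, which matches the 2800 stated (2580 without the correction). Expected events: 2800 × 0.009 = 25.2 and 2800 × 0.018 = 50.4.

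**2. Which events are exposed.**

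| Channel | Depends on unblinded D28 questioning? |
|---|---|
| Coded GP records (9.1) | No; same in both periods |
| Diary requests at days 7 and 14 (12.5.2) | No; after both in-person visits |
| Hospital admissions by 24-hour line, email or eDiary, via uMed (12.5.2, 14.7) | No |
| Non-GP, non-admitted attendances in days 15-28 | Mainly yes |

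Section 16.2 allows e-diary entries for up to 28 days after dosing, so even the last row may be partly covered, although no request is scheduled after day 14. The diary row rests on Section 12.5.2. Appendix A lists e-diary information at D0 and diary review at D28 for the EV group, but at D28 and D56 for the LV group. Read literally, diary handling there follows the LAIV period in each arm, so these passages need reconciling.

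**3. Size if questioning differs by product.** The documents give neither the non-GP share nor capture rates, so all of these are assumptions:
- non-GP share of wheeze events 20-40%, spread evenly over 28 days, so the share in days 15-28 is f = 0.10-0.20;
- period 1 capture of exposed events 0.95 after LAIV and c = 0.70-0.80 after placebo;
- period 2 capture 0.80 after either product;
- all other events fully captured; true relative risk 1.

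Period 1: RR = (1 − f + 0.95f)/(1 − f + cf). Pooled: add the period 2 term (1 − f + 0.80f) to numerator and denominator.

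| f | c | Period 1 | Pooled |
|---|---|---|---|
| 0.10 | 0.80 | 0.995/0.980 = 1.02 | 1.975/1.960 = 1.01 |
| 0.10 | 0.70 | 0.995/0.970 = 1.03 | 1.975/1.950 = 1.01 |
| 0.20 | 0.80 | 0.990/0.960 = 1.03 | 1.950/1.920 = 1.02 |
| 0.20 | 0.70 | 0.990/0.940 = 1.05 | 1.950/1.900 = 1.03 |

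Swapping the capture rates between products inverts these: 0.95-0.98 in period 1 and 0.97-0.99 pooled.

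**4. Scale against sampling error.** With 25.2 events per condition and no effect, the standard error of the log relative risk is about √(1/25.2 + 1/25.2) = 0.28, ignoring within-child correlation. The largest pooled bias above is log(1.026) = 0.026, or 0.026/0.28 ≈ 9% of one standard error.

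**5. Change of instrument alone.** Let the overall captured fraction be g1 in period 1 and g2 in period 2, the same for both products. With 1:1 allocation each product is given equally often in each period, so the pooled ratio is RR × (g1 + g2)/(g1 + g2) = RR. With non-GP capture of 100% in period 1 and 70% in period 2, a true 1.00 stays 1.00 and a true 2.00 stays 2.00.

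**The case against.** The strongest reply is that unblinded delivery is openly declared (single blinded in the title; Sections 12.4 and 13.1.3), that the main outcome source never passes through site staff, and that Section 16.5 requires complete verification of primary endpoint data. Most of this stands, and it is why the effect is small. Verification limits what staff can choose to record, but it cannot recover an attendance that was never elicited.

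A reader might infer more than the documents support:
- **That every non-GP attendance is exposed.** Applying the same formula to the full 20-40% gives 1.03-1.11 in period 1 and 1.02-1.06 pooled. This ignores the diaries, which cover the first half of each period, and the separate admission line.
- **That the bias must inflate the LAIV risk.** The sign comes entirely from the assumed capture rates. Staff could prompt or record more after LAIV, or less.
- **That using two instruments biases the result.** On its own the change is a period difference balanced across products. How the carry-over check in Section 15.2 would treat such a difference is a separate question.
- **That D56 is free of unblinded staff.** The local team contacts non-responders, so the contrast between periods is one of degree.

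**Conclusion.** The point holds in limited form. One component of the primary outcome is elicited at D28 by people who know and can see the allocation, with no safeguard on who asks or on the order of events. The exposure is mainly non-GP, non-admitted attendances in days 15-28 of period 1. Under the stated assumptions a null relative risk moves by about 2-5% in period 1 and 1-3% pooled, in a direction that cannot be known in advance. That is small beside the target relative risk of 2 and beside sampling error. The case for acting is that this unblinded route into a safety endpoint is avoidable, not that it threatens the trial's conclusion. The size would change with the true non-GP share, diary completion and use of the admission line, none of which the protocol quantifies.

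**What to change.** Send the same uMed questionnaire shortly before D28 as at D56, and have it completed and locked before the eCRF displays the allocation. If it has not been completed beforehand, the parent completes it at the visit before the allocation is shown.

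Flag any event first reported to unblinded staff after that point, keep it in the safety data, and run the primary outcome with and without flagged events as a sensitivity analysis. Removing such events from the primary outcome outright would be debatable in a safety trial, because it discards real wheeze and makes period 1 depend on questionnaire response.

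Cost: one more send of a questionnaire already planned for D56, with prompts for those who do not answer, and a change in the order of eCRF forms. Sample size, the in-person visits and clinical management do not change.
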